# PROTOCOL SYNOPSIS

Title	CONTOUR: Con dition of Submental Fullness and T reatment Ou tcomes R egistry (A Registry of Submental Fullness, Treatment Options Administered, and Associated Outcomes)					
Protocol Number	ATX-101-15-40M					
Phase	4					
Objectives	The primary objective of this registry is to develop a comprehensive understanding of the condition of submental (SM) fullness due to submental fat (SMF), how it is treated in current clinical practice, and the risks and benefits associated with its treatment. This objective will be accomplished through the systematic collection of data on the following:  • Practice patterns of physicians with patients who have SMF concerns  • The population of patients who are eligible for SMF reduction treatment  • Eligible patients who elect SMF reduction treatment  • Treatment procedures  • Treatment outcomes  • Safety profile through adverse event reporting of the SMF reduction treatments					
	administered					
Study Design	This is a prospective, observational, multi-center registry. Patients enrolled in this study will provide information related to the condition and treatments of interest and will permit their physicians to provide any available data concerning their condition status and treatment, as indicated in the table of Data for Collection.					
Treatment Procedures	The eligibility of patients for treatment, and the treatment administered, will be determined by the physician. Treatments will be administered by the physician or qualified designee (other care provider, such as nurse practitioner or physician assistant) according to their directions at each center.					
Rationale	SM fullness associated with the accumulation of SMF can influence negative self-perception. While the SM region is visually important, at present, only surgical options (cosmetic surgery, liposuction) are available to reduce SMF. Currently available injectable products, ie, botulinum toxins and dermal fillers, are employed primarily in the aesthetic rejuvenation of the upper and mid-face and do not adequately address contouring the SM region. The use of energy based devices for lipolysis has been investigated as a less invasive approaches; but may still require accompanying surgery in more severely affected cases, and safety concerns remain. Recently, a pharmacologic treatment, deoxycholic acid injection (ATX-101) was approved by the FDA for improvement in the appearance of moderate to severe convexity or fullness associated with submental fat in adults.					
	This registry will gather information on patterns of use and outcomes of treatments for SM fullness by reduction of SMF, beginning with currently used methods, and including newly approved products as they become adopted into the practice.					
Duration of Registry	Data collection is anticipated to continue for approximately 15 months. The duration of individual patient participation will vary depending on the chosen treatment method and individual requirements.					

Protocol ATX-101-15-40M Amendment 2: 20 Oct 2015

Patient Population and Key Selection Criteria	
 
Adult male and female patients, aged 18 years and above, presenting with SM fullness due to the accumulation of unwanted SMF, and considered by their treating physician to be a candidate to receive treatment of SM fullness by reduction of SMF. If the patient decides to participate, then the following will be performed or assessed:
 
Signed informed consent and medical records release
 
No severe skin laxity, defined as superficial wrinkling, loose skin separated from deeper neck structures, and/or marked skin redundancy (draping and/or sagging), per the physician's judgment
 
No other cause of fullness in the SM region (eg, thyroid enlargement, cervical adenopathy) other than localized SMF
 
Not participating in an interventional clinical study, currently or within 30 days before enrollment
 
Did not previously participate in an interventional clinical study involving ATX-101
 

Number of Patients	Approximately 1000 patients will be recruited from approximately 100 sites in the US and Canada.
Study Procedures	Details of the physician's practice setting will be recorded once for each site; treatment logistics will be recorded at the first treatment session for each patient.  Patients considering treatment for improvement of SM fullness due to SMF will be recruited. Eligible patients will be enrolled in the registry and data will be collected from patients who elect treatment until their SMF reduction treatment is completed or discontinued. Patients who do not initially elect treatment will be followed to determine whether or not they subsequently undergo treatment, and if not, until up to one year has elapsed since enrollment and no treatment has been elected. Physicians will treat and assess patients according to their discretion.  At enrollment, data on previous relevant SMF and facial aesthetic treatment(s) will be collected from the patients, and as necessary, their medical records, along with baseline SMF assessments and information on treatment goals. Demography (birth date, sex, race, ethnic origin), Clinical Information (height, weight, lifestyle habits), and a brief medical history (including diabetes, cardiovascular disease) will be collected, Information including treatment received for SMF reduction, treatment procedures and outcomes, follow-up assessments of SMF, and adverse events (AEs) will be recorded at subsequent clinic visits or telephone contacts (Data for Collection). Patient medical history data will be updated, as appropriate, at the first treatment visit.
Data Collection Procedures	Electronic data capture (EDC) will be used for participating sites to record clinical data, data questionnaires and assessment data via electronic case report forms (eCRFs) accessed through a secure internet portal. Data entry screens will be designed to efficiently capture the desired data elements from patient medical records (Data for Collection).
Data Elements	Physician Practice Profile At each site, the physician will complete the Physician Practice Setting Questionnaire, including the following information:  • Physician characteristics:  - Clinical history / specialty, including board certification  - Years of aesthetic practice  - Percent of practice focused on facial aesthetics  - Physician approach to discussing new treatment options  - Number and roles of physicians and other healthcare providers (HCPs) in the

Protocol ATX-101-15-40M Amendment 2: 20 Oct 2015

practice

- Aesthetic treatment options, including options for reducing SMF, offered by the clinic: types and relative frequencies
- Consent and intake details pertaining to aesthetics and chin and neck (cervicomental) region.
- Percent of patients presenting with SMF concerns and percent receiving SMF reduction treatment
- Referral of patients for SMF reduction treatment to or from other physicians

#### **Patient Population (all patients)**

Upon confirmation of eligibility and signed informed consent, the following information will be collected at the Enrollment visit for all patients:

- Informed consent / medical records release
- Demography & Clinical Information (birth date, sex, race, ethnic origin, height, weight, , lifestyle habits)
- Brief medical history (including diabetes, cardiovascular disease)
- Patient treatment history:
  - o Previous facial aesthetic treatment(s) within past 24 months:
  - o Treatment type (eg, toxins, fillers, devices, cosmetic surgery)
  - o Location of treatment (eg. face, chin/neck)
- Patient Treatment Goals Questionnaire:
- History of SMF concern
- Patient's treatment goals in terms of aesthetic outcome
- Physician Treatment Goals Questionnaire
  - Physician's treatment goal in terms of aesthetic outcome
- Enrollment SMF assessments:
- Clinician-Reported Submental Fat Rating Scale (CR-SMFRS) score
- Patient-Reported Submental Fat Rating Scale (PR-SMFRS) score
- Patient-Reported Submental Fat Impact Scale (PR-SMFIS) score
- Submental Skin Laxity Grade (SMSLG) score
- Subject Self Rating Scale (SSRS) score
- Self-perception of age (SPA) scale score

Should a patient elect to receive treatment for SMF reduction, the site will also record:

- Treatment decision date(s)
- SMF reduction treatment type(s) selected

#### **Treatment Logistics (treated patients)**

At each site, for patients who elect treatment for SMF reduction (treated patients), the physician or designee will complete the following questionnaires and scales at the first treatment session(s) for each treatment selected (unless otherwise stated) for all treated patients:

#### • Treatment Logistics Questionnaire

Completed at the first treatment session for patients who elect treatment for SMF reduction (treated patients):

- Time spent by HCPs with patients, discussing treatment details and expectations
- HCP who prepared the treatment materials/equipment, HCP who prepared the patient for the procedure, and HCP who performed the procedure

Protocol ATX-101-15-40M Registry Study Protocol Amendment 2: 20 Oct 2015

- Other treatments (if any) combined in the same treatment session / area(s) and where these treatments were administered
- Clinic scheduling procedures for treatment session

#### • Pain Numeric Rating Scale for Pain:

At each treatment time point (Baseline, Follow-up, End-of-Treatment), all treated patients will be asked to provide a Pain Numeric Rating Scale score for the maximum pain experienced post-treatment by the patient.

For patients treated with ATX-101, patients will be asked to provide a Pain Numeric Rating Scale score for maximum pain experienced post-treatment by the patient at every treatment session.

#### • Treatment Procedures Questionnaire

At each treatment session (for patients treated with ATX-101 only), the site will complete the Treatment Procedures Questionnaire, including the following information:

- Comfort regimen used, type and effectiveness, pre- and post-treatment
- Protocol for post-treatment follow-up (eg, phone, visit) for each treatment session
- Total time spent by patients on treatment and post-treatment follow-up in office (including deviation from the scheduled time / other treatments given during the same appointment)
- Time interval between treatments
- Details of treatment method (treatment dependent)
- Patient Grid Questionnaire

#### **Adverse Events**

To be collected only for patients who elect treatment for SMF reduction. The following information will be recorded in the Electronic Data Capture (EDC) system:

- Frequency, severity, duration, medication or other treatment required, and outcome of adverse events (AEs) during and after each SMF reduction treatment session:
  - At each visit, patients will have treatment areas examined and be interviewed in an open-ended manner to solicit reports of AEs since the last visit.
  - Patient calls to clinic with post-treatment concerns or symptoms that meet the definition of AEs (eg, pain, swelling, bruising, numbness, induration) will be included in the AE record.

#### **Treatment Outcomes and Follow-up**

Following SMF reduction treatment initiation, patients and physicians will be asked to complete SMF assessments and scales at the **Follow-up** time point for each treatment:

- Clinician-Reported Submental Fat Rating Scale (CR-SMFRS) score
- Patient-Reported Submental Fat Rating Scale (PR-SMFRS) score
- Patient-Reported Submental Fat Impact Scale (PR-SMFIS) score
- Submental Skin Laxity Grade (SMSLG) score
- Subject Self Rating Scale (SSRS) score
- Pain Numeric Rating Scale for Pain: maximum pain experienced post-treatment by the patient.

After each treatment completed, patients and physicians will be asked to complete the following SMF assessments, questionnaires, and scales for End-of-Treatment time point:

Clinician-Reported Submental Fat Rating Scale (CR-SMFRS) score

Protocol ATX-101-15-40M Amendment 2: 20 Oct 2015

	Patient-Reported Submental Fat Rating Scale (PR-SMFRS) score
	Patient-Reported Submental Fat Rating Scale (FR-SMFIS) score      Patient-Reported Submental Fat Impact Scale (PR-SMFIS) score
	Submental Skin Laxity Grade (SMSLG) score
	Subject Self Rating Scale (SSRS) score
	Dei (CICD (CA) (CDA)
	
 
Patient Self-Perception of Age (SPA) scale score
 
Patient Global Questions
 

	Patient Global Questions     Patient End-of-Treatment Questionnaire, including the following information:
	
 
After treatment, would the patient undergo the treatment again? (eg, was the benefit greater than the risk)
 

	- After treatment, would the patient recommend this treatment to a friend?
	- Overall, is the patient aesthetically satisfied with the treatment outcome?
	
 
Did the patient's friends, spouse or co-workers notice a positive/negative aesthetic change?
 

	
 
Physician End-of-Treatment Questionnaire, including the following information: Physician's treatment goal in terms of aesthetic outcome: was the physician's treatment goal achieved?
 

	Pain Numeric Rating Scale for Pain: maximum pain experienced post-treatment by the patient.
	Clinical Information (height, weight)
	For patients that do not elect treatment for SMF reduction (untreated patients), patients will be asked to complete:
	Patient End-of-Study Questionnaire to capture the patient reasons for not electing treatment(eg, benefits did not outweigh the risks for the treatment options, too expensive, etc.)
	Clinical Information (height, weight)
Statistical Methods	A formal statistical analysis plan (SAP) that will provide details of all analyses and presentation of registry data will be approved prior to data analysis.
	Descriptive statistics will comprise the number of observations (n), mean, standard deviation (SD), median, minimum, and maximum for continuous variables; and n and percent for categorical variables, with the number of patients who do not have missing values as the denominator.
	No imputation for missing data will be performed. Analyses will be conducted using observed cases.
Sample Size	Up to 1,000 patients are anticipated. The number and size of analysis groups will be determined by the treatments selected by the patients in this sample; therefore, group sizes may not be identical. In general, if the sample size in a treatment cohort is at least 250, this study is well-powered to observe an improvement of at least one grade in the CR-SMFRS (Section 8.1)
Analysis Populations	Analyses will be based upon all patients who were enrolled and have at least one post-baseline visit. Additional subgroups also may be examined, as deemed appropriate (eg, sex, initial assessment scores, prior treatments received).
Practice, Patient, and Treatment Data	Data will be summarized, by type of SMF reduction treatment, with descriptive statistics, and presented in listings.
Outcome Data	SMF Assessments
	Results for SMF assessments will be summarized with descriptive statistics at each time point. Changes from baseline will be summarized descriptively for each

CONFIDENTIAL

gistry Study Protocol

treatment cohort at each post-baseline assessment. Exploratory analysis of covariance (ANCOVA) methods will also be used to assess change from baseline at the end-of-treatment follow-up timepoint, where treatment type and baseline score will be included in the model. The ANCOVA results will be generated in SAS using PROC MIXED. Cochran-Mantel-Haenszel (CMH) tests for association, stratified by site, will be used to assess categorical responses. The qualification for a "responder" for each SMF assessment will be further defined in the SAP. For the CR-SMFRS and PR-SMFRS assessments, the number and percent of patients in each treatment cohort who have at least a 1-grade improvement will be presented, along with the corresponding 95% confidence interval (CI). Responses to the other SMF assessments will be summarized similarly.

Protocol ATX-101-15-40M

Amendment 2: 20 Oct 2015

Questionnaire responses will be summarized using counts, percents, and 95% CIs for each treatment type.

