# 8.1 Sample Size

Up to 1000 patients are anticipated. No pre-specified statistical hypotheses will be tested, therefore no formal power calculations were performed. Instead, the precision of 95% confidence intervals around key response variables was estimated. Note that the number and size of analysis groups will be determined by the treatments selected by the patients in this sample; therefore, group sizes may not be identical.

Table 1 below provides 2-sided 95% confidence interval (CI) around an expected response rate of 67.5% for CR-SMFRS score in patients treated with ATX-101 during Phase 3 clinical trials, where response was defined as an improvement of at least one grade.

Table 1 Precision and 95% Confidence Intervals for Various Sample Sizes, Based on an Expected Patient Response Rate of 67.5%

Sample size (N) 250	95% CI 61.7, 73.3	500	63.4, 71.6
750	64.1, 70.9		

Table 2 below provides the 2-sided 95% CI around expected levels of patient satisfaction rates. 13

Table 2 Precision and 95% Confidence Intervals for Various Combinations of Sample Size and Patient Satisfaction Rates

	Probable Rates of Patient-reported Satisfaction				
_	80%	85%	90%		
Sample Size (N)	95% CI	95% CI	95% CI		
250	75.0, 85.0	80.6, 89.4	86.3, 93.7		
500	76.5, 83.5	81.9, 88.1	87.4, 92.6		
750	77.1, 82.9	82.4, 87.6	87.9, 92.1		

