# 8.2.2 Analyses

Data will be summarized, by type of SMF reduction treatment, with descriptive statistics, and presented in listings. No formal statistical hypotheses are established for this protocol, but exploratory analyses involving inferential tests will be performed as described below.

Demographic and baseline characteristics will be summarized. Post-baseline values and change from baseline in selected outcome variables will be summarized, by type of SMF reduction treatment, with descriptive statistics, and, where appropriate, graphical presentations, and presented in listings.

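### The synopsis calls a cohort of 250 well-powered and cites Section 8.1, which says no power was calculated and gives only confidence-interval precision

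*Protocol*

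**What the plan says.** The protocol makes two statements about sample size, and the first cites the second.

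- **Protocol Synopsis, Sample Size row:** "if the sample size in a treatment cohort is at least 250, this study is well-powered". The effect it names is a gain of one grade or more on the CR-SMFRS, and Section 8.1 is given in brackets as the source.
- **Protocol Section 8.1:** "No pre-specified statistical hypotheses will be tested, therefore no formal power calculations were performed". The next sentence gives the actual basis: "Instead, the precision of 95% confidence intervals around key response variables was estimated". Table 1 uses an expected response rate of 67.5%, taken from Phase 3 experience with ATX-101, "where response was defined as an improvement of at least one grade". Table 2 does the same for patient satisfaction rates of 80%, 85% and 90%.

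Section 8.2.2 is consistent with Section 8.1: "No formal statistical hypotheses are established for this protocol, but exploratory analyses involving inferential tests will be performed". The tests in question, in Section 8.2.2.1, are an exploratory ANCOVA with treatment type and baseline score in the model, and CMH tests stratified by site.

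**The concern.** Power belongs to a test: it is the probability of rejecting a stated null when a stated alternative is true. The synopsis claims adequate power at 250 patients, but the section it relies on denies that any such calculation was made. Both statements cannot stand.

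The wording has a second difficulty. An improvement of one grade or more is the rule that classifies an individual patient as a responder. It is not a difference between groups, nor a distance from a reference rate, so it cannot serve as the effect that a cohort of 250 is powered to find.

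What is at stake is how the registry is described. The synopsis is the part most often read alone, and it also announces the exploratory ANCOVA and CMH tests. A favourable power statement beside them suggests a validated cohort size where only interval width was examined.

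**Working it through.** **Inputs.** From Protocol Section 8.1: expected response rate p = 0.675; n = 250, 500 and 750; two-sided 95% confidence. Satisfaction rates for Table 2: 0.80, 0.85 and 0.90.

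**Step 1: reproduce Table 1.** The normal-approximation (Wald) interval is p ± 1.96 × √(p(1 − p)/n).

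- n = 250: √(0.675 × 0.325 / 250) = 0.02962; half-width 1.96 × 0.02962 = 0.0581; interval 61.69% to 73.31% (stated 61.7, 73.3).
- n = 500: half-width 4.11 points; interval 63.39% to 71.61% (stated 63.4, 71.6).
- n = 750: half-width 3.35 points; interval 64.15% to 70.85% (stated 64.1, 70.9).

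All nine Table 2 intervals reproduce to one decimal by the same formula. For example, 80% at n = 250 gives 75.04% to 84.96% (stated 75.0, 85.0). Section 8.1 contains no numerical error.

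**Step 2: look for the ingredients of a power statement.**

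| Needed for power | Given in the synopsis sentence or Section 8.1? |
|---|---|
| Null value or comparator | No |
| Significance level of a test | No (95% is the confidence level of the intervals) |
| Alternative at group level | No (67.5% is an expected rate, with nothing to set it against) |
| Target power | No |

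If a mean change of one grade was meant instead, Section 8.1 gives no standard deviation from which to work. No power figure can be reproduced because none was produced.

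**Step 3: show that the claim has no fixed value.** Suppose the true rate is 67.5%, n = 250, and an exact one-sample binomial test is run at one-sided 0.025. The null rates below are assumptions for illustration only; the protocol states none.

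| Assumed null rate | Power |
|---|---|
| 50% | above 99.9% |
| 55% | 97.9% |
| 57.5% | 89.3% |
| 60% | 67.2% |
| 65% | 11.8% |

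The same 250 patients are amply powered or hardly powered at all, depending on a number that the protocol does not give.

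**The case against.** The strongest defence is that this is loose wording in a summary. The sentence is hedged as a general statement, concerns a single cohort and names no comparator. It reads most naturally as shorthand for the Table 1 precision at the smallest tabulated size. The cited section corrects it at once, Section 8.2.2 repeats that there are no formal hypotheses, and the ANCOVA is labelled exploratory. No enrolment target, endpoint or decision rule depends on the sentence.

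Most of this stands, and it limits the severity. It does not reconcile the two statements: a precision result has been described as power, and the cited section expressly disclaims power.

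A reader might go further, in ways the protocol does not support:

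- **That no inference is planned, or that it is planned only between treatment types.** Section 8.1 excludes pre-specified hypotheses only. Exploratory tests are planned, and so are 95% intervals within each cohort for responders (Section 8.2.2.1) and for questionnaires (Section 8.2.2.2).
- **That the registry is underpowered by a stated amount for comparing treatments.** Any such figure needs a comparator size and a difference that the protocol does not give. A simple two-proportion calculation would also not represent the site-stratified CMH test or the ANCOVA on change scores.
- **That the total of up to 1000 caps the number of cohorts that can reach 250.** Patients may select more than one treatment, with assessments repeated for each, so cohorts can overlap.
- **That a non-significant contrast will be presented as equivalence.** The protocol makes no equivalence or non-inferiority claim.

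**Conclusion.** The point holds as an internal inconsistency of modest severity. The synopsis claims power at 250 patients per treatment cohort and cites a section that says power was not calculated. The claim lacks every element needed to define it and treats the patient-level responder definition as a detectable effect.

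It is tempting to call this an arithmetic error, but no figure is wrong: Tables 1 and 2 are correct, and 250 is their smallest sample size. What Section 8.1 supports at that size is a half-width of about 5.8 percentage points around 67.5%. That rests on the Wald formula, which reproduces the tables, and on the Phase 3 response rate applying to the cohort in question.

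The contradiction itself needs no assumption. Both statements are in the protocol, so a statistical analysis plan could not make both true.

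**What to change.** Replace the power sentence in the Sample Size row of the synopsis with:

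> With 250 patients in a treatment cohort, the two-sided 95% CI around an expected CR-SMFRS response rate (at least one-grade improvement) of 67.5% is 61.7% to 73.3%, a half-width of about 5.8 percentage points (Section 8.1); no power is claimed, including for the exploratory comparisons between treatment types.

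Sections 8.1 and 8.2.2 need no change. The cost is one synopsis sentence and a less favourable description of the sample size. Design, data collection and analysis are unaffected.
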